### **Exploratory Efficacy Analyses**

The exploratory efficacy endpoints for the current trial include:

- Average Asthma DSS during the peak RS;
- Average Asthma DSS during the entire RS;
- Average Asthma DSS during the whole treatment period;
- Average daily number of puffs of as-needed SABA used during the peak RS;
- Average daily number of puffs of as-needed SABA used during the entire RS;
- Average weekly number of nights with nocturnal awakening due to asthma symptoms requiring SABA use during the peak RS;
- Average weekly number of nights with nocturnal awakening due to asthma symptoms requiring SABA use during the entire RS.

These endpoints will be analyzed using the same ANOVA model as the primary efficacy endpoint. Asthma DSS related endpoints will be analyzed based on the FAS population, while SABA use and nocturnal awakening related endpoints will be analyzed based on subjects with asthma in the FAS population.

In addition, components of the rhinoconjunctivitis DSS (ocular symptoms and nasal symptoms) will be summarized for the peak RS and the entire RS.

Moreover, the exploratory efficacy analyses will only consider the rescue medications provided by the study (i.e., reported in the e-diary). Some subjects may take rescue medications that are not provided by the study. A sensitivity analysis will be conducted for the following endpoints by including these rescue medications:

- Average daily number of puffs of as-needed SABA used during the peak RS;
- Average daily number of puffs of as-needed SABA used during the entire RS.

[Table 3] summarizes the key analysis strategy for the efficacy/immunologic endpoints.

Table 3 Efficacy/Immunologic Endpoints

Endpoint	Statistical Method a	Analysis Population	Missing Data
Primary Efficacy Endpoint			
Average TCS during the peak RS	ANOVA	FAS	Observed data only
			LOCF
		PP	Observed data only
	Wilcoxon Rank Sum Test; Hodges-Lehmann estimate of treatment difference c	FAS	Observed data only
	Longitudinal Data Analysis	FAS	Model based
Key Secondary Efficacy Endpoints			
Average TCS during the entire RS	ANOVA	FAS	Observed data only
Average rhinoconjunctivitis DSS during the peak RS	ANOVA	FAS	
Average rhinoconjunctivitis DMS during the peak RS	ANOVA	FAS	
	Zero-inflated log-normal c		
Tertiary Efficacy/Immunologic Analyses			
Average rhinoconjunctivitis DSS during the entire RS	ANOVA	FAS	Observed data only
Change from baseline in IgE level against Ambrosia artemisiifolia at Visit 6 and Visit	constrained Longitudinal	FAS	Model based
Change from baseline in IgG 4 level against Ambrosia artemisiifolia at Visit 6 and Visit	constrained Longitudinal	FAS	Model based
Exploratory Efficacy Analyses			
Average Asthma DSS during the peak RS, the entire RS, and the whole treatment	ANOVA	FAS	Observed data only
Average daily number of puffs of as-needed SABA used during the peak RS and the entire RS	ANOVA	FAS (asthma only)	Observed data only
Average weekly number of nights with nocturnal awakening due to asthma symptoms requiring SABA use during the peak RS and the entire RS	ANOVA	FAS (asthma only)	Observed data only
ANOVA = Analysis of Variance; DSS = Daily Symptom Score; DMS = Daily Medication Score; FAS = Full Analysis set; IgE = immunoglobulin E; IgG 4 = immunoglobulin G 4 ; LOCF = Last non-missing observation carried forward; PP = Per Protocol; RS = Ragweed Season; SABA = short- acting beta 2 -agonist; TCS = Total Combined Score.			
a Details of the statistical models are described in Section 3.2.5.			
b Missing data from both treatment groups will be imputed using the sample distribution of TCS observed from the placebo group.			
c This method will be applied if excessive zeros are observed in the data.			

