3.3.2 Exploratory Objective

Objective: To explore the effect of MK-3641 versus placebo on asthma endpoints in those subjects with asthma and those without asthma.

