7.1.2.11 Complete/Review Daily Symptoms in e-Diary

The subject/parent/guardian will be required to record allergy and asthma symptoms in an e-diary once daily, preferably in the evening before bedtime, from Visit 4 to Visit 8. Subjects should be instructed to record the worst severity rating for each symptom during the 24-hour recall period. For example, if the subject experienced severe itchy eyes for only 10 minutes during the past 24 hours and mild itchy eyes for the rest of the past 24-hour period, the subject should record ‘Severe Symptoms’ on the e-diary for the day. In the rare case that the subject/parent/guardian cannot complete the e-diary at their regular time, they will be allowed to complete the daily e-diary up to 9 am the following morning. An e-diary will be issued at Visit 4 and collected at Visit 8. Instructions on how to complete entries and e-diary findings will be reviewed with the subject/parent/guardian at all visits.

A total of nine symptoms, six rhinoconjunctivitis symptoms (runny nose, stuffy nose, sneezing, itchy nose, itchy eyes, and watery eyes) and three asthma symptoms (cough, wheeze, chest tightness/shortness of breath [dyspnea]) will be measured on a scale of 0 to 3 as follows:

0 = no symptoms	No sign/symptom evident
1 = mild symptoms	Sign/symptom is clearly present but minimal awareness; easily tolerated
2 = moderate symptoms	Definite awareness of sign/symptom, which is bothersome but tolerable
3 = severe symptoms	Sign/symptom is hard to tolerate; may cause interference with activities of daily living and/or sleeping

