#### **Exploratory Efficacy Endpoints**

- Average Asthma DSS during the peak RS, the entire RS, and the whole treatment period;
- Average daily number of puffs of as-needed SABA used during the peak RS and the entire RS;

- Average weekly number of nights with nocturnal awakening due to asthma symptoms requiring SABA use during the peak RS and the entire RS.

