##### **3.2.5.1 Statistical Methods for Efficacy/Immunologic Analyses**

###### **Primary Efficacy Analysis**

The primary efficacy endpoint for the current trial is the average TCS during the peak ragweed season. It will be analyzed using the ANOVA model, which includes fixed effects of treatment, baseline asthma status (yes, no), age group (5 to 11 years, 12 to 17 years), pollen season, and pollen region nested within pollen season. Pollen region will be defined based on pollen station and may include several sites within an acceptable distance between the pollen counters and corresponding sites.

Two-sided 95% CI of the treatment difference in adjusted means will be presented. Also, the treatment difference in adjusted means relative to the adjusted mean of the placebo group will be presented as a percentage with corresponding 2-sided 95% CI derived using the bootstrap method. No missing data will be imputed.

The normality assumption of the ANOVA model will be checked using the Shapiro-Wilk test and inspection of the Q-Q plot. If a severe violation is observed, the primary analysis will be based on Wilcoxon Rank Sum test; the p-value will be reported together with the associated Hodges-Lehmann estimate of the treatment difference and its 2-sided 95% CI. Also, the difference in the treatment group medians relative to the median of the placebo group will be presented as a percentage with the corresponding 2-sided 95% CI derived using the bootstrap method.

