### 3.2.9 Subgroup Analyses and Effect of Baseline Factors

Analysis for the primary efficacy endpoint will be provided for the following subgroups of baseline factors:

- Baseline asthma status (yes, no);
- Age group (5 to 11 years, 12 to 17 years);
- Gender (male, female);
- Race (Caucasians, non-Caucasians);

- ICS use for subjects with asthma (yes, no);
- Allergen sensitization type (ragweed only, ragweed + others);
- Geographic region (e.g., US, Canada, Europe). Region classification for each study site will be determined before database lock.

In addition, subgroup analysis on the primary efficacy endpoint will be provided for:

- Pollen counts (low, high): The subgroups will be defined based on the median of the subject level accumulated pollen counts during the first 21 days of the pollen season;
- Local application site reaction (had local application site reactions, did not have local application site reactions).

The same ANOVA model as in the primary efficacy analysis will be applied for the subgroup analyses.

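### The plan specifies no asthma DSS effect by asthma status, so no asthma endpoint has an efficacy estimate in subjects without asthma; the added treatment-period window is only partly covered by the diary

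*SAP*

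**What the plan says.** - **Objective.** Protocol 3.3.2: "To explore the effect of MK-3641 versus placebo on asthma endpoints in those subjects with asthma and those without asthma".
- **Collection.** Under Protocol 4.2.3.1.2, all subjects complete the asthma DSS daily from Visit 4. Only subjects with asthma record SABA puffs and nocturnal awakenings.
- **Population.** sSAP 3.2.5.1, Exploratory Efficacy Analyses: "Asthma DSS related endpoints will be analyzed based on the FAS population", whereas "SABA use and nocturnal awakening related endpoints will be analyzed based on subjects with asthma in the FAS population". Table 3 of the sSAP and Protocol 8.2.5.1 agree.
- **Model.** "These endpoints will be analyzed using the same ANOVA model as the primary efficacy endpoint". That model has "fixed effects of treatment, baseline asthma status (yes, no), age group (5 to 11 years, 12 to 17 years), pollen season". Its one remaining term is a nested effect of region. No treatment-by-asthma-status term is listed.
- **Subgroups.** sSAP 3.2.9: "Analysis for the primary efficacy endpoint will be provided for the following subgroups of baseline factors", with baseline asthma status first in the list. Protocol 8.2.8 has the same limit.
- **Windows.** Protocol 8.2.3.1 gives asthma DSS two windows, the peak and the entire ragweed season. sSAP 3.2.3.1 gives three: "Average Asthma DSS during the peak RS, the entire RS, and the whole treatment period". The third is not defined.
- **Diary.** Protocol 7.1.2.11 has the subject or parent "record allergy and asthma symptoms in an e-diary once daily, preferably in the evening before bedtime, from Visit 4 to Visit 8". Dosing starts at Visit 2 (Protocol 5.2.2).

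**The concern.** The objective names two groups, and the analysis of the only asthma endpoint measured in both returns a single treatment difference averaged over them. If the effect differs by asthma status, the planned output cannot show it. A reader looking for the result in children without asthma would find none for any asthma efficacy endpoint. If the split is not written down before database lock, any by-status result would have to be reported as post hoc under the sSAP's own rule (3.2).

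The window is a separate and smaller matter. A result labelled as covering the whole treatment period would be taken to include the first weeks of dosing, for which no diary asthma score exists in any subject.

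**Working it through.** **1. Objective against planned output.** sSAP 3.2.5.1 lists seven exploratory endpoints.

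| Endpoint | Windows | Recorded by | Analysed in | Estimate with asthma | Estimate without asthma |
|---|---|---|---|---|---|
| Asthma DSS | 3 | all subjects | FAS, pooled | none | none |
| SABA puffs | 2 | asthma only | asthma only | yes | not possible |
| Nocturnal awakenings | 2 | asthma only | asthma only | yes | not possible |

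So 4 of the 7 endpoints address the objective in subjects with asthma. None addresses it in subjects without asthma, and asthma DSS is the only one that could.

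**2. What the pooled model estimates.** Write p for the share of subjects with asthma, and dA and dN for the treatment differences with and without asthma. Randomisation is 1:1 and stratified by asthma status (Protocol 5.3, 5.4), so a model with asthma status as a main effect only gives approximately

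p × dA + (1 − p) × dN.

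This single number does not identify dA or dN. The documents give no value for p.

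**3. Treatment duration (the plan's own figure).** Protocol 2.1 gives 12 to 20 weeks of pre-seasonal treatment plus about 8 weeks in season: 12 + 8 = 20 and 20 + 8 = 28. This reproduces the stated 20 to 28 weeks.

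**4. Part of treatment before the diary starts.** Visit timings are from the Trial Flow Chart (Protocol 6.0). Visit 3 is at week 4 (+7 days). Visit 6 is about 2 weeks before the season (±7 days). Visit 4 is midway between them, and at most 6 to 8 weeks after Visit 3. With P pre-seasonal weeks:

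Visit 6 = P − 2; Visit 4 = (4 + P − 2)/2; unrecorded share = Visit 4 / (P + 8).

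| P (weeks) | Visit 6 | Visit 4 | Total weeks | Unrecorded share |
|---|---|---|---|---|
| 12 | 10 | 7 | 20 | 7/20 = 35% |
| 16 (assumed midpoint) | 14 | 9 | 24 | 9/24 = 37.5% |
| 20 | 18 | 11 | 28 | 11/28 = 39% |

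The extremes use the visit windows and allow 0 to 1 extra week of dosing up to Visit 8:

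- Lowest: P = 12, Visit 3 at week 4, Visit 6 at week 9. Visit 4 = (4 + 9)/2 = 6.5, and 6.5/21 = 31%.
- Highest: P = 20, Visit 3 at week 5, Visit 6 at week 19. Visit 4 = (5 + 19)/2 = 12, and 12/28 = 43%.

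The diary therefore covers about 61% to 65% of treatment at nominal times (57% to 69% with windows). Asthma DSS is analysed on observed data only (sSAP Table 3), so the computed quantity is a Visit 4 to Visit 8 average.

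**The case against.** The objective does not say that the groups are to be reported separately. It can be read as a statement of scope: asthma endpoints are explored in everyone, and pooling asthma DSS over the FAS meets that. This reading is possible, but a sentence that names both groups is more naturally taken to mean each of them.

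The rest of the opposing case limits the point rather than removing it.

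- A reader might infer that the plan fails its objective altogether. It does not: SABA use and awakenings address it in subjects with asthma. AE summaries by asthma status are also planned (sSAP 3.2.5.2), although these are safety output.
- A reader might infer a known loss of effect from pooling, or that opposite effects cancel. Neither is supported. If the effect were confined to subjects with asthma, the pooled estimate would keep a fraction p of it. As p is not given, any percentage only restates the share assumed, and nothing in the documents suggests opposite effects.
- A reader might infer that the added window has no diary data. More than half of it is covered, and the peak-season and entire-season windows are untouched. Early asthma events would still be seen through AE monitoring and the Comment Card; only the diary score is missing.
- Exploratory analyses carry nominal p-values (sSAP 3.2.5). Asthma status is recorded, so the by-status result could be recovered later, though as a post hoc analysis.

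**Conclusion.** The point holds as a gap in an exploratory analysis. Followed as written, the plan produces no asthma DSS effect by asthma status and no efficacy estimate for any asthma endpoint in subjects without asthma. This rests on reading the objective as referring to each group.

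The window is mainly a labelling correction. At nominal visit times about the first 35% to 39% of treatment has no asthma DSS, or 31% to 43% with visit windows. These figures assume that Visit 4 falls at the midpoint as scheduled and no later than 8 weeks after Visit 3.

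The primary endpoint, the fixed testing sequence, the power and the type I error are not affected, and the documents give no ground for reading the point as a threat to them.

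**What to change.** In sSAP 3.2.5.1 and Table 3, for the asthma DSS endpoints, add a treatment-by-baseline-asthma-status term to the existing ANOVA. Report the treatment difference with its 95% CI in each stratum, labelled exploratory and nominal. Fitting by stratum would also serve. The interaction term is the safer choice, because the pollen regions already had to be merged to avoid convergence failure (sSAP 3.1.1) and separate fits would thin them further. Use status at baseline, so that a child diagnosed with asthma during the trial stays in the original stratum.

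Rename the third window *Visit 4 to Visit 8 (or discontinuation)* wherever it appears.

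The cost is small: six estimates (three windows by two strata) and a label change, with no new data, since asthma status is already a randomisation factor. sSAP 3.2 allows changes to exploratory analyses before database lock, so no protocol amendment is needed.

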**Handling of Missing Data**

The missing data approaches are specified for the primary efficacy endpoint sensitivity analyses (including multiple imputation, LOCF, and model based) and immunologic endpoints (model based). All other analyses will be conducted based on the observed data only. Proportion of subjects with missing data will be summarized for each efficacy/immunologic endpoint.

### 3.2.5.2 Statistical Methods for Safety Analyses

Safety and tolerability will be assessed by clinical review of all relevant parameters including adverse experiences (AEs), laboratory tests, and vital sign measurements.

The analysis of safety results will follow a tiered approach [Table 4]. The tiers differ with respect to the analyses that will be performed. Tier 1 safety endpoints will be subject to inferential testing for statistical significance with p-values and 95% CIs provided for between- group comparisons. Tier 2 safety endpoints will be evaluated via point estimates and 95% CIs for between-group comparisons. Tier 3 safety endpoints will be evaluated via point estimates only.

For this trial, Tier 1 safety endpoints include:

- Proportion of subjects reporting pre-specified local application site reactions (including adverse events related to lip swelling/edema, mouth swelling/edema, palatal swelling/edema, swollen tongue/edema, oropharyngeal swelling/edema, pharyngeal edema/throat tightness, oral pruritus, throat irritation, tongue pruritus, and ear pruritus);
- Proportion of subjects reporting anaphylaxis and/or systemic allergic reactions;
- Proportion of subjects treated with epinephrine.

For the analysis of “Proportion of subjects treated with epinephrine”, the denominator will include all subjects in the ASaT population, regardless of whether self-injectable epinephrine was provided or not. Meanwhile, a sensitivity analysis will be conducted where the denominator will include subjects in the ASaT population who were provided with self-injectable epinephrine, and the numerator will be subjects from the denominator subjects who were treated with epinephrine.

Tier 2 safety endpoints for this trial include:

- Proportion of subjects with any AE;
- Proportion of subjects with any serious AE;
- Proportion of subjects with any drug-related AE;
- Proportion of subjects with any serious and drug-related AE;
- Proportion of subjects who discontinue due to an AE;
- Proportion of subjects with specific AEs or SOCs (incidence  $\geq$  1% subjects in one or more of the treatment groups).

The Tier 1 and Tier 2 safety endpoints will be analyzed using the stratified Miettinen and Nurminen method [1985] with baseline asthma status and age group as stratification

factors.

Tier 3 safety endpoints for this trial include:

- Change from baseline in laboratory test parameters at each post-baseline visit;
- Change from baseline in vital sign parameters at each post-baseline visit;
- Change from baseline in pulmonary function test parameters at each post-baseline visit;
- Summaries by SOC for general AEs, serious AEs, drug-related AEs, serious and drug-related AEs, and AEs resulting in discontinuation;
- Average duration of AEs in minutes on Day 1;
- Average duration of AEs in days over Day 2 to Day 14;
- Average duration of AEs in days over Day 15 to Day 28.

Point estimates will be provided for the Tier 3 safety endpoints. In addition, AE summaries (general AEs, serious AEs, drug-related AEs, serious and drug-related AEs, and AEs resulting in discontinuation) by asthma status will also be provided. For pulmonary function test parameters, a cLDA model-based analysis will also be conducted (see Section 3.2.5.1 for more details about the cLDA model).

[Table 4] summarizes the safety tier and level of analysis for the safety endpoints.

Table 4 Analysis Strategy for Safety Parameters

Safety Tier	Safety Endpoint a	p-Value	95% CI for Treatment Comparison	Descriptive Statistics
Tier 1	Proportion of subjects reporting pre-specified local application site reactions (including adverse events related to lip swelling/edema, mouth swelling/edema, palatal swelling/edema, swollen tongue/edema, oropharyngeal swelling/edema, pharyngeal edema/throat tightness, oral pruritus, throat irritation, tongue pruritus, and ear pruritus);  Proportion of subjects reporting anaphylaxis and/or systemic allergic reactions;  Proportion of subjects treated with epinephrine.	X	X	X
Tier 2	Any AE; Any Serious AE; Any Drug-Related AE; Any Serious and Drug-Related AE; Discontinuation due to AE; Specific AEs or SOCs b (incidence $\geq$ 1% of subjects in		X	X
Tier 3	Change from baseline in laboratory test parameters at each post-baseline visit; Change from baseline in vital sign parameters at each post-baseline visit; Change from baseline in pulmonary function test parameters at each post-baseline visit; Summaries by SOC for general AEs, serious AEs, drug-related AEs, serious and drug-related AEs, and AEs resulting in discontinuation; AE summaries by asthma status; Average duration of AEs in minutes on Day 1;  Average duration of AEs in days over Day 2 to Day 14; Average duration of AEs in days over Day 15 to			X
AE = adverse event; CI = confidence interval; SOC = System Organ Class; X = results will be provided. a Adverse Experience references refer to both Clinical and Laboratory AEs. b Includes only those endpoints not pre-specified as Tier 1 or Tier 2 endpoints.				

In addition, the SLIT Report Card (Section 4.2.3.2 of the protocol) will be completed by the subject/parent/guardian, daily for the first ~28 days of dosing, to collect information on local side effects of SLIT that occur within the first 60 minutes after each daily study drug intake. Adverse events identified by the WAO as local side effects of SLIT include the following: dysgeusia, oral pruritus, swelling of lips, mucosal edema, ear pruritus, swollen tongue, glossodynia, mouth ulceration, tongue ulceration, throat irritation, pharyngeal edema, nausea, abdominal pain upper/abdominal pain, vomiting, and diarrhea.

Identified local AEs will be graded via a programmatic approach and clinical review as mild, moderate, or severe. An exploratory review of the intensity grading via 2 different methods, the programmatic approach using the WAO grading system and grading as determined by the investigator’s review of the AEs with their subjects/parents/guardians, will be conducted.

The WAO grading system for SLIT local adverse events defines intensity as follows:

Mild (Grade 1)	Not troublesome and no symptomatic treatment required and no discontinuation of SLIT because of local side effects
Moderate (Grade 2)	Troublesome or requires symptomatic treatment and no discontinuation of SLIT because of local side effects
Severe (Grade 3)	Grade 2 and SLIT discontinued because of local side effects

The WAO local AE intensity grading was modified in that subjects collect the information on the presence of the AEs on the SLIT Report Card but do not indicate if they consider the AE “troublesome” or “not troublesome.” Subjects also indicate if a medication is utilized to treat the AE and information regarding discontinuation due to the AE is also collected. The WAO intensity grading for local AEs will be determined programmatically. Essentially, mild intensity (Grade 1) will be assigned to events that do not result in symptomatic use of a medication. If an AE results in use of a symptomatic medication to treat the AE, it is assigned an intensity of moderate (Grade 2) and considered troublesome; if an AE results in the use of a symptomatic medication and in discontinuation from treatment, it is assigned an intensity of severe (Grade 3).

